As secondary objectives, we will determine if milrinone improves oxygenation at 48 h and 72 h post-infusion, reduces right ventricular pressures on echocardiogram, and alters the risk of systemic hypotension, arrhythmias, intracranial hemorrhage, need for extracorporeal membrane oxygenation (ECMO), and chronic lung disease (CLD, defined as oxygen need at 28 d of postnatal age). Finally, we will also evaluate the infant's medical (pulmonary and nutritional) status at discharge and conduct a phone questionnaire at 4, 8, and 12 months of age.

Study Design: Double-blind randomized controlled pilot trial with 1:1 (treatment: control) randomization.

Eligibility criteria:

Infants are eligible if they meet all of the following criteria:

- (i) ≥ 36 0/7 weeks postmenstrual age (PMA) at birth by best obstetric estimate AND birth weight of ≥ 2000 g
- (ii) postnatal age ≤ 7 days (168 hours of age, including post-operative infants with HRF)
- (iii) invasive mechanical ventilation (defined as ventilation with an endotracheal tube) and
- (iv) one arterial blood gas with an OI ≥ 10 (after tracheal tube obstruction, pneumothorax and other easily resolvable mechanical causes for increased OI are ruled out) on the most recent arterial blood gas within 12 hours prior to the time of randomization.
- (v) if an arterial blood gas is not available at the time of randomization, a preductal OSI of ≥ 5 can be used as an inclusion criterion instead of OI ≥ 10 ; (the OSI should be based on the most recent preductal pulse oximetry recording and must be within 12 hours of randomization)
- (vi) postnatal blood gas with $\text{PCO}_2 \leq 80$ mmHg (arterial, capillary or venous blood gas) on the most recent blood gas sample obtained within 12 hours prior to randomization

Note: Criteria (iv) to (vi) must be met at the most recent analysis within 12 hours prior to randomization.

Stratification: Patients will be stratified based on severity of HRF using the prediction formula ($\text{PaO}_2/\text{FiO}_2$ ratio – PaCO_2 value) at the time of randomization. (Park, Lee et al. 2013) Patients with prediction value ≥ 0 will be considered as “moderate” and infants with a value of < 0 as “severe” HRF. If no arterial blood gas is available prior to randomization, an oxygen saturation index (OSI – see below) of 5 to 10 is considered “moderate” HRF and > 10 is considered “severe” HRF.

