2.2. SPECIFIC AIMS

Specific aim #1 - Efficacy: To determine the acute changes in oxygenation and echocardiography during treatment with IV milrinone (improvement in OI/OSI and PaO₂ at 24 hours from baseline and changes in right ventricular pressure and function at 24 – 72 h from baseline)

Specific aim #2 - Safety: To determine the safety of IV milrinone treatment by comparing the incidence of serious adverse events (severe hypotension, bleeding - intracranial and extracranial hemorrhage and arrhythmias).

Specific aim #3 - Outcome: To determine the infant's status (pulmonary and nutritional) at discharge and conduct a series of telephonic surveys at 4, 8 and 12 months of postnatal age to assess the impact of baseline characteristics (gender, gestational age at birth, mode of delivery, birth weight, time of diagnosis – antenatal vs. postnatal), study intervention and other therapies and interventions on infant's status.

Specific aim #4 - Feasibility: To derive preliminary estimates of the incidence of survival without ECMO in the control and IV milrinone treatment groups and to demonstrate the feasibility of conducting a large randomized controlled clinical trial.

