3.2. SECONDARY OUTCOMES

- (i) Oxygenation response at 24 h after initiation of study drug assigning a minimum OI of 40 or OSI of 20 (if no arterial blood gas is available) for subjects that need ECMO or die after initiation of study drug infusion but prior to 24h of study-drug infusion. In this analysis if the patient's OI is 30 (or OSI of 15) and is cannulated for ECMO due to hemodynamic instability, he/she will be assigned an OI of 40 (or OSI of 20). However, if the OI prior to ECMO is 47 (i.e., > 40), the higher number (47) will be used for analysis of this secondary outcome.
- (ii) Oxygenation index at 48 and 72 h after initiation of study drug (or OI/OSI at the time of initiation of ECMO or immediately prior to death, for infants placed on ECMO or died before these time points),
- (iii) Change in echocardiographic findings – velocity of tricuspid regurgitation, left ventricular ejection fraction, position of the interventricular septum and direction of shunt at the PDA and PFO level – prior to and 24-72h after starting the study

medication. This outcome will be available only for those infants who have a pre-study drug echocardiogram and a second echocardiogram between 24-72 h after initiation of study drug. These data will be extracted from echocardiograms performed for clinical indications.

- (iv) Vasoactive Inotrope score and systemic blood pressure
- (v) Area under the curve for inspired oxygen after initiation of the study drug over the first 72 hours of study-drug infusion (or prior to ECMO or death, whichever is earlier) (Note: inspired oxygen and ventilator data from 4 time points per day – every 6 hours will be recorded to calculate area under the curve),
- (vi) If subsequent to the study drug, any additional inotrope or pulmonary vasodilator is used (such as iNO), we will evaluate the oxygenation response to these agents. If inotropes or vasodilators were used prior to the initiation of study drug, similar values will be recorded. The OI (or OSI) and $\text{PaO}_2/\text{FiO}_2$ ratio prior to and after initiation of the inotrope / vasodilator are recorded (these data are recorded at 6 hour intervals; the date and time of initiation of individual inotropes and vasodilators is recorded). The change in OI (or OSI) and $\text{PaO}_2/\text{FiO}_2$ ratio in response to these agents is evaluated as a continuous variable and arbitrarily classified into responders, partial responders and non-responders similar to prior trials (1997, 1997).

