 - a. complete response is defined as an increase in $\text{PaO}_2/\text{FiO}_2$ ratio $> 20 \text{ mmHg}$ from baseline,
 - b. partial response is an increase in $\text{PaO}_2/\text{FiO}_2$ ratio of 10 to 20 mmHg from baseline,
 - c. no response is defined as an increase of $< 10 \text{ mmHg}$ (or a decrease) in $\text{PaO}_2/\text{FiO}_2$ ratio from baseline,
 - d. the site of sampling (preductal vs. postductal) is also recorded. (Gien and Kinsella 2016); right radial and ulnar arterial lines/sticks will be considered preductal; Left radial and ulnar arterial samples are usually preductal but can occasionally be postductal; umbilical arterial lines and posterior tibial lines (both sides) are always postductal.
 - e. in patients without arterial access, an OSI (oxygen saturation index) will be used
- (vii) Supplemental oxygen at 28 d, and 56 d (or discharge, whichever comes earlier) from the hospital – primary institution or secondary institution to which patient was transferred. The use of supplemental oxygen at 28 d will be used to calculate the incidence of chronic lung disease. Chronic lung disease severity will be classified similar to the BPD classification in preterm infants at > 32 week gestation (Jobe and Bancalari 2001). Intermittent supplemental oxygen given only during feedings or for spells administered for < 60 minutes and if the infant is not receiving oxygen at any other time during the day will not be considered as “supplemental oxygen”.

- a. Time point of assessment: 28 d, 56 d postnatal age or discharge to home whichever comes first.
- b. Mild CLD: treatment with oxygen > 21% oxygen for at least 28 days but breathing room air by 56 days' postnatal age or discharge to home whichever comes first.
- c. Moderate CLD: need for > 21% but < 30% oxygen at 56 days postnatal age or discharge to home whichever comes first.
- d. Severe CLD: need for \geq 30% oxygen and/or positive pressure (high-flow nasal cannula – defined for the purpose of this study as > 2 LPM, non-invasive ventilation or nasal intermittent positive pressure ventilation – NIV or NIPPV, CPAP, or positive pressure ventilation) at 56 days' postnatal age or discharge whichever comes first.

(viii) Survival to discharge (or day 120, whichever comes earlier) without ECMO and

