5.4 STATISTICAL ANALYSIS PLAN

Baseline data will be collected prior to randomization including gestational age, side of the diaphragmatic hernia, birth weight, mode of delivery and arterial blood gas parameters (oxygenation index-OI) and/or pulse oximetry data (oxygen saturation index-OSI). Data from a baseline clinical echocardiogram is recorded (if performed prior to study drug initiation or within 2h of initiation of study drug). During the infusion of study drug, arterial blood gas parameters and hemodynamic data (blood pressure, heart rate and echocardiography results) will be recorded. After completing the study infusion, surgical details, and mortality information will be collected. Among survivors, respiratory and nutritional status at discharge and at 4, 8 and 12 months of age will be collected.

Data will be presented as mean \pm SD for normally distributed variables and as median and ranges (with percentiles) for non-normally distributed data. All analysis will be by intention-to-treat. Baseline characteristics will be compared between treatment groups using chi-square and Fisher's exact test for discrete variables and t-test and ANOVA for continuous variables. The primary outcome, difference from baseline OI at 24 h, will be compared between treatment groups using a general linear model adjusted for the stratification factor of HRF severity. Other continuous outcomes will be analyzed similarly. Models for longitudinal outcomes such as oxygenation and vasoactive inotrope scores (short-term) and nutritional and pulmonary outcomes at 12 months (long-term) will include the effect of time, the interaction between time and treatment, and random effects to account for the correlation between measures taken on the same individual over time. Categorical outcomes will be analyzed using analogous generalized linear models. Cox regression models (with adjustment for HRF severity) will be used to plot proportion of responders who survive without ECMO against survival time in hours. Analyses may adjust for clinical site if treatment assignments are severely imbalanced for some sites provided that it is computationally feasible to do so. The potential influence of baseline measures such as time of diagnosis – antenatal vs. postnatal, side of the defect, and gender on pulmonary and nutritional outcome will be explored through the use of additional models similar to those described above.

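### The only time-to-event analysis of survival without ECMO is worded for responders, a largely post-randomisation subset, and conflicts with the intention-to-treat rule in the same section

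*Combined protocol and SAP*

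**What the plan says.** - **Time-to-event analysis.** Section 5.4 has one sentence on it. Cox models with adjustment for HRF severity "will be used to plot proportion of responders who survive without ECMO against survival time in hours". The sentence gives no treatment term, time origin or censoring rule, and does not say who counts as a responder.
- **General rules in the same paragraph.** "All analysis will be by intention-to-treat", and "Categorical outcomes will be analyzed using analogous generalized linear models". Neither carries a responder condition.
- **The outcome.** Section 3.2 (viii) is "Survival to discharge (or day 120, whichever comes earlier) without ECMO", without a responder condition.
- **The aim.** Specific Aim 4 in section 2.2 is "To derive preliminary estimates of the incidence of survival without ECMO in the control and IV milrinone treatment groups", again without one.
- **The only responder classes.** Section 3.2 (vi) concerns other inotropes or pulmonary vasodilators: "we will evaluate the oxygenation response to these agents". The change in OI or OSI and in PaO2/FiO2 is "arbitrarily classified into responders, partial responders and non-responders similar to prior trials". The cut-offs are a rise in PaO2/FiO2 of more than 20 mmHg, of 10 to 20 mmHg, or less than that. Similar values are recorded for agents started before study drug.

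**The concern.** The outcome and the aim concern both randomised groups. The only survival model that serves them is worded for a narrower set. If the sentence is followed as written, an infant enters the curves by receiving another agent and responding to it. Where that agent follows study drug, milrinone may affect both its use and the response. A drug that changes who responds also changes the severity mix of responders in each arm, so a difference between arms among responders need not reflect the drug's effect on ECMO or death.

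At stake is a probably prominent display of the outcome that section 5.5.3.2 names as the primary outcome of the definitive trial. There is also a practical problem. The general rule and the specific sentence point to different populations, so an analyst could follow either one and claim to have followed the plan.

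**Working it through.** **1. Which population does each statement imply?**

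| Place | Item | Population |
|---|---|---|
| 2.2, Aim 4 | Incidence of survival without ECMO | Both randomised groups |
| 3.2 (viii) | Survival without ECMO, yes/no | No restriction |
| 5.4, general rule | All analyses | Intention-to-treat |
| 5.4, categorical outcomes | Generalized linear model, analogous to the HRF-adjusted primary model | No restriction |
| 5.4, Cox sentence | Time to ECMO or death | Responders |

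Only the last row departs from the others.

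**2. Can the responder set be built from the text?** Not reproducibly. The classes in 3.2 (vi) apply to infants who received another agent, so the rest have no class. The Cox sentence does not say whether partial responders count. Some classifications may rest on agents started before study drug, so the set is largely, not wholly, post-randomisation.

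**3. The plan's own figures for death or ECMO (section 5.1).** No figure is stated for the Cox analysis. The nearest is 376 per arm for 40% v 30%, power 0.8, alpha 0.05. The two-proportion formula gives

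n = [1.96·√(2·0.35·0.65) + 0.8416·√(0.4·0.6 + 0.3·0.7)]² / 0.1² ≈ 356,

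and the continuity correction gives 356/4·[1 + √(1 + 4/(356·0.1))]² ≈ 376. The stated figure reproduces with that correction. It rests on proportions, not on a hazard ratio.

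**4. What would an all-infant Cox model deliver?** With 33 per arm at 40% v 30%, expected events are 33·0.4 + 33·0.3 = 23.1. Under proportional hazards HR = ln(0.7)/ln(0.6) = 0.70. Schoenfeld power is Φ(√(23.1/4)·|ln 0.698| − 1.96) = Φ(−1.10) ≈ 14%. For 80% power, 4·(1.96 + 0.8416)²/(ln 0.698)² ≈ 244 events are needed. The repair corrects the comparison; it does not create a powered test.

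**5. How large could the distortion be?** The documents give no response share and no link between response and severity, so this is illustration only. Assume milrinone has no effect on death or ECMO (40% in both arms), and that a standard normal severity drives both outcome and response on the logit scale, with slope 0.5 (weak), 1 (moderate) or 2 (strong). The HR is ln(1 − p_milrinone)/ln(1 − p_control) among responders.

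| Response, control v milrinone | Link | Death/ECMO among responders, control v milrinone | Gap (points) | Spurious HR |
|---|---|---|---|---|
| 40% v 40% | any | equal | 0 | 1.00 |
| 40% v 60% | weak | 36.8% v 37.9% | 1.1 | 1.04 |
| 40% v 60% | moderate | 30.1% v 33.2% | 3.1 | 1.13 |
| 40% v 60% | strong | 17.9% v 24.5% | 6.5 | 1.42 |
| 30% v 60% | weak | 36.3% v 37.9% | 1.6 | 1.06 |
| 30% v 60% | moderate | 28.5% v 33.2% | 4.8 | 1.21 |
| 30% v 60% | strong | 14.8% v 24.5% | 9.7 | 1.75 |

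(Gaps are from unrounded rates.) In these scenarios about 26 to 33 of the 66 infants remain, with about 5 to 12 events.

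A second model gives the same picture. It takes response 40% v 65%, an event logit slope of 1.5, and a chosen correlation between response and severity. With overall risk 40%, responders show 19.8% v 27.4% at correlation −0.8, 27.6% v 32.5% at −0.5 and 32.6% v 35.6% at −0.3. With overall risk 63% (36/57, section 2.3.3, Table 6), the gap at −0.8 is 42.2% v 51.7%, or 9.5 points.

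If milrinone truly lowers the rate from 40% to 30%, the first model with a moderate or strong link shows differences among responders from −6.1 to +1.1 points, instead of −10.

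**The case against.** **The clinical outcome is still analysed by intention to treat.** This stands. Outcome (viii) is yes/no and falls under the generalized linear model sentence. Section 5.1 plans its precision as a proportion with a 95% confidence interval for 33 infants, and the definitive-trial size is also based on proportions. A reader might infer that the key clinical outcome as a whole loses the protection of randomisation, or that a biased hazard ratio would drive the sizing of the definitive trial. The documents support neither.

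**The sentence describes a plot, and the word may be loose.** This stands in part. No treatment term or test is named, and responders may be a slip for infants meeting outcome (viii), or may point to a descriptive display for outcome (vi). The defect is therefore a conflict between two statements, not a proven intention to exclude non-responders. The intention-to-treat statement does not remove the conflict, because the specific sentence still names a different population.

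**The illustrated gaps depend on the inputs.** This stands. At 40% overall risk and slope 1.5, the second model's gap falls to 3.9 points at correlation −0.4 and 2.0 at −0.2. It is zero when response shares are equal. The simulations also omit the HRF adjustment, which would probably remove part of the bias. A figure of 7 to 10 points quoted alone would be close to the worst case.

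**Immortal time.** An infant must live long enough to be classified, so a reader might infer immortal-time bias. That chiefly distorts a comparison of responders with non-responders, which the plan does not state. Between arms within responders, both arms carry the same requirement.

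**Conclusion.** The concern holds for the time-to-event analysis only. As worded, the Cox sentence applies to a set that the plan does not define for this purpose, that is formed largely after randomisation, and that disagrees with the intention-to-treat rule, outcome (viii) and Aim 4. Any comparison of arms inside that set would be non-randomised.

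The size of the bias cannot be derived from the documents. For a drug with no effect, the illustrations run from 0 to about 10 points of spurious harm. That range rests on assumed response shares and an assumed severity link; the mechanism needs only that milrinone changes who responds and that response tracks severity. The primary outcome, OI change at 24 h, is not affected, and section 5.1 already states that the pilot is not powered to compare death or ECMO. The wording should be corrected before the analysis, but it does not threaten the trial's main result.

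**What to change.** In section 5.4, remove the restriction to responders and replace the Cox sentence with wording such as:

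> Time from randomisation to the first of ECMO or death, through discharge or day 120 (whichever is earlier), will be shown by randomised arm with Kaplan-Meier curves and analysed with a Cox model including treatment and HRF severity, in all randomised infants.

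Add a censoring rule, including how infants discharged alive without ECMO before day 120 are handled. Keeping them event-free to day 120 would match outcome (viii), which counts them as successes.

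If a responder display is kept, define responder (which agent, which change, whether partial responders count), label the display descriptive, and start its clock at the response assessment.

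The cost is one or two sentences of analysis wording. No new data are needed, and neither the sample size nor the primary analysis changes.

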5.5 DATA MONITORING PLAN

The DSMC will monitor the progress of the trial on a routine basis for monitoring enrollment progress and reviewing the accruing safety data. The DSMC will meet to look over the preliminary data after enrolling the first 10 subjects. Interim reviews are scheduled via e-mail or teleconference if DSMC identifies any emerging safety issues. A suggested schedule for further meetings based on subject enrollment is as follows:

25% enrollment (~ 17 subjects),
50% enrollment (33 subjects)
75% enrollment (~ 50 subjects)
Completion of enrollment (~ 66 subjects)

5.5.1 Reporting Adverse Events

There is high morbidity and mortality associated with the natural course of CDH. The following measures will be used to monitor safety of the trial based on a review of adverse events. Adverse event reporting will be handled as follows:

- (i) **Potential Adverse Events** (as defined below) will be reported on the Adverse Events form.
- (ii) Because of the nature of the study population, mild events will not be recorded as adverse events unless they are also unexpected.
- (iii) Potential adverse events listed below that are severe, life-threatening or result in death (as per the MOP toxicity table) will be entered in the electronic data capture system (EDC) within 24 hours of discovery.
- (iv) **Serious Adverse Events** will be reported on the Adverse Events form, entered in the electronic data capture system (EDC) and reported to NICHD and the NRN data center within 24 hours of discovery (via SAE Narrative)
when:
 - a) they result in death **or**
 - b) they are possibly, probably or definitely related to the intervention **or**
 - c) they are unexpected. An unexpected event is defined as an adverse event not known to be associated with the natural course of CDH or a specified side-effect of interventions in the management of CDH.
- (v) All serious adverse events that meet one of the above criteria will be reviewed by the NICHD NRN Program Scientist (as medical monitor).
- (vi) All serious events that are marked as at least possibly related to the intervention will be forwarded to the Chair of the independent NRN DSMC for any further action.

The duration of reporting adverse events would include the period of administration of the study drug and 24 hours' post-infusion. This period will cover approximately 6 half-lives of milrinone and plasma levels are expected to be undetectable by 24 hours after completion of study-drug infusion.

